6.4.3 Secondary Efficacy Endpoint

- Surfacer System advancement from femoral vein to sub-clavicular exit to facilitate CVC placement assessed by the ability of the Surfacer System to facilitate central venous access placement.

6.4.4 Secondary Safety Endpoint

- Technique Conversion rate.

7.0 STUDY PROCEDURES

7.1 Informed Consent

Potential subjects will be provided with study information and given an opportunity to ask questions about the study and treatment options. If the individual agrees to participate; they will complete a written informed consent, be assigned a unique study identifier, and undergo screening and baseline assessments. Study identifier will include the site number and a sequential subject ID number (i.e. 05-04).

7.2 Screening and Baseline Assessments

Screening and Baseline assessments will include the following:

- Inclusion and Exclusion Criteria

- Medical history with demographics
- Physical exam with vital signs
- TCVO Lesion Type Determination
- Medications (antithrombotic and cardiovascular)
- Pregnancy test (not required if patient is male or non-child bearing potential)
- Clinical laboratory tests including coagulation profile (APTT, PT, INR), CRP, LDH, ASAT, ALAT, fibrinogen, D-dimer
- Ultrasound or venous duplex venography of upper body veins (SVC, jugular, inferior vena cava (IVC), brachiocephalic and subclavian) to rule out acute thrombosis within a vein to be crossed by the Surfacer System
- AP and LAT chest x-ray or cine fluoroscopy will be performed prior to the procedure to define the pattern of occlusion and to rule out acute thrombosis
- 12-lead ECG

7.2.1 Screen Failures

If the Principal Investigator determines that the subject is not an acceptable study candidate at any time during screening and the collection of baseline study data, up to the point of enrollment, the subject will be documented as a Screen Failure and no further study data will be collected. The reason and cause for Screen Failure will be documented.

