Biffi R.	2009	-	-	136	0%	136	0%		-		-		-
Bertogli S	1996	424	4.2%		-	424	1.4%	424	7.5%		-		-
Smith H.O.	1995	133	3.8%		-	133	3%		-		-		-
FEMORAL		Arterial Puncture		Misplacement		Pneumo-thorax		Hematoma		Hemothorax		Mechanical complications**	
Author	Year	Pts	%	Pts	%	Pts	%	Pts	%	Pts	%	Pts	%
Hingwala J.	2014		-		-		-		-		-		-
Alexandrou E.	2014	163	4.3%	163	0%	163	0%		-	163	0		-
Yeral M.	2013		-		-		-	45	0%		-		-
Parienti J.J.	2008		-		-		-	370	1.1%		-		-
Lorente L.	2008		-		-		-		-		-	184	7.61%
Al-Hwiesh, A.K.	2007											14	14.3%
Montagnac R.	1997		-		-		-		-		-	55	3.63%
Bertoglio S.	1996	41	2.4%		-	41	0%	41	7.2%		-		-

**Mechanical complications include arterial puncture, malposition, local haematoma, pneumothorax, haemothorax, air embolism, arrhythmias, accidental removal and failure of catheterization. Similarly, other mechanical complications are vessel perforation, atrial perforation and catheter malfunctions (Karkee, 2010). Note: complication or data not analysed/mentioned in the articles are indicated with a dash (-).

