6.0 STUDY DESIGN

This study has been designed as a prospectively enrolled, single-arm, multicenter study to demonstrate the safety and efficacy of the BVT Surfacer System in patients who require central venous access.

A total of 30 subjects is planned at a minimum of three (3) sites. Ten subjects will be enrolled initially. After safety data review, enrollment is expected continue to 30 subjects overall with no more than 10 subjects enrolled at a single site.

Enrolled subjects will undergo the Surfacer System procedure, then exit the study after follow-up at hospital discharge and 7-days post procedure. BVT will utilize an Independent Data Monitoring Committee (IDMC) to review the study’s safety data during the conduct of the study and at study closure.

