7.3 Subject Enrollment

A subject will be considered “enrolled” in the study when they have completed informed consent, are qualified per all study screening requirements and component of the investigational study device is inserted into the subject.

Once a subject has been exposed to the study device, even if the Investigator is unable to complete the Surfacer treatment, the study subject will be considered part of the intent-to-treat population and will be followed up to 7 days post-procedure, or until any adverse events are resolved.

See Section 8.0 for description of analysis populations and statistical considerations.

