8.0 STATISTICAL CONSIDERATIONS

8.1 Introduction

This is a prospective, single-arm, multi-center study to demonstrate the safety and efficacy of the Surfacer® System. Clinical data will be obtained from up to 30 subjects treated with the Bluegrass Vascular Technologies Surfacer System device at a minimum of three (3) sites.

No site will enroll more than 10 subjects. The study population will include patients who are candidates for vascular access with limited or diminishing upper body venous access or pathology impeding standard access methods. Patients who provide consent will be enrolled and undergo the procedure with follow-up at hospital discharge and 7 days post-procedure. Total study duration is anticipated to be 12 months. The study objectives and analytical methods to be used are described herein.

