8.3 Statistical Analysis

8.3.1 Data Reporting Convention

Descriptive statistics will be utilized to summarize the demographic and baseline data.

For continuous endpoints, descriptive statistics will be presented including the number of subjects with the measurement, mean, standard deviation, median, minimum and maximum.

For categorical endpoints, descriptive statistics will include the number with the event or characteristic, the number evaluated, the percentage presented, and 95% exact binomial confidence interval. A critical two-sided alpha level of 0.05 will be carried out for all statistical evaluations.

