8.3.4 Analysis Populations

Enrolled Population:

Study results will be analyzed and reported for all enrolled patients who sign the informed consent, complete the screening procedures are eligible and enrolled in the study.

Intent-to-treat (ITT) Population:

The ITT safety subject population comprises all enrolled subjects in whom Surfacer System usage was attempted (i.e. the first step in the Instructions for Use of the Surfacer System was performed), regardless of whether or not the procedure was completed with the successful placement of a CVC.

Per Protocol Population:

The per protocol (PP) population will include all enrolled subjects in whom the Surfacer System procedure was completed, with a CVC implanted completely and correctly (i.e. the last step in the Instructions for Use of the Surfacer System was performed).

All primary and additional endpoints will be evaluated in both the intent to treat (ITT) and Per Protocol analysis sets. The intent to treat analysis will be considered primary.

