9.0 SAFETY

Safety monitoring will be performed by the Principal Investigator during the conduct of this study. An Adverse Events (AE) will be recorded and assessed from the time of enrolment through study completion or early withdrawal. All AEs will be followed by the Principal Investigator until resolution or stabilization.

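### Enrolment, and with it adverse event recording and ITT membership, starts only when a device component is inserted, so harms and stopped attempts during femoral access can go uncounted

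*Combined protocol and SAP*

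**What the plan says.** Section 7.3 makes enrolment depend on three things: consent, meeting the screening requirements, and that a "component of the investigational study device is inserted into the subject". It adds that a subject exposed to the device stays in ITT and is followed to day 7 even if the procedure cannot be completed.

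Section 8.3.4 makes ITT the primary set and restricts it to enrolled subjects "in whom Surfacer System usage was attempted (i.e. the first step in the Instructions for Use of the Surfacer System was performed". Section 9.0 says adverse events are "recorded and assessed from the time of enrolment through study completion".

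Section 7.2.1 deals with candidates judged unacceptable during screening and baseline: "up to the point of enrollment, the subject will be documented as a Screen Failure and no further study data will be collected". The reason is still documented.

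Other sections read differently. Section 8.1 says "Patients who provide consent will be enrolled and undergo the procedure", which puts enrolment at consent. Sections 1.3 and 7.4 list adverse events among the intra-procedural data without giving a start time.

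The second primary safety endpoint (6.4.2, 8.2.1) covers anticipated events related to the device or the procedure and compares them with historical data from central venous placement.

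**The concern.** Section 3.3 describes site preparation, sedation, local anaesthesia and femoral guidewire access before the Workstation Sheath goes in. Table 3 lists that sheath as a device component. There is therefore a period in which the study procedure is under way but, under 7.3, the subject is not yet enrolled.

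Two things can be lost there.

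- **Harms of access.** An arterial puncture while femoral access is being gained comes before enrolment. Under 9.0 as written it is not recorded, even if the procedure continues and the subject enters ITT. The subject then counts in the denominator and the event does not count in the numerator.
- **Stopped attempts.** A subject whose procedure ends in the window is not enrolled, is not in ITT, and has no assigned adverse event recording or 7-day visit.

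The historical rates in 5.1 and Table 9 include arterial puncture and hematoma. The footnote to the mechanical complications column also lists "accidental removal and failure of catheterization". If the study starts counting later in the procedure than an access complication can occur, the comparison loses part of its meaning.

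**Working it through.** **1. Order of events in the text**

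| Step | Source | Enrolled under 7.3? | Adverse events recorded under 9.0? |
|---|---|---|---|
| Consent | 7.1 | No (8.1 suggests yes) | No |
| Sedation, femoral access, guidewire | 3.3 | No | No (1.3 and 7.4 suggest yes) |
| Workstation Sheath inserted | 3.3, Table 3 | Yes | Yes |
| Crossing the occlusion, exit, catheter placement | 3.3 | Yes | Yes |

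Sections 7.3 and 8.1 cannot both define enrolment. Section 8.3.4 adds another trigger, the first step in the Instructions for Use. Those instructions are not among the documents, so it cannot be settled whether that step precedes insertion.

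The window could also be where some subjects are found ineligible. Exclusion 1 in 6.3.2 covers occlusion of the right femoral and right iliac veins. The screening ultrasound in 7.2 names upper-body veins and the inferior vena cava, but not the femoral or iliac veins. Such an occlusion might first appear at femoral access. This is an inference.

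**2. The plan's own figure**

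Inputs: n = 30 (6.0: "A total of 30 subjects is planned at a minimum of three (3) sites") and two-sided alpha 0.05 (8.3.1). The Clopper-Pearson limits for x of n are the 0.025 quantile of Beta(x, n − x + 1) and the 0.975 quantile of Beta(x + 1, n − x).

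- 27/30: 73.5% to 97.9%
- 15/30: 31.3% to 68.7%

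Both agree with 8.2.2.

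**3. Efficacy if the target is all attempted procedures**

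Let k be the number of eligible subjects stopped before insertion and counted as failures. The rate is x/(30 + k). The documents give no value for k, so 0 to 2 is assumed.

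| k | From 27 successes | From 30 successes |
|---|---|---|
| 0 | 27/30 = 90.0% (73.5 to 97.9) | 30/30 = 100% (88.4 to 100) |
| 1 | 27/31 = 87.1% (70.2 to 96.4) | 30/31 = 96.8% (83.3 to 99.9) |
| 2 | 27/32 = 84.4% (67.2 to 94.7) | 30/32 = 93.8% (79.2 to 99.2) |

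From 27/30 the difference is 2.9 points for one such subject and 5.6 for two.

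**4. Safety in subjects who go on to insertion**

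A pre-insertion event that is not recorded, in a subject with no other counted event, lowers the event rate by 1/30 = 3.3 points. This can only favour the device.

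For scale, 5.1 gives femoral arterial puncture at 2.4% to 4.3% and femoral hematoma at 0% to 7.2%. If those rates applied here (an assumption), the expected numbers in 30 subjects would be:

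- arterial puncture: 30 × 0.024 = 0.7 to 30 × 0.043 = 1.3
- hematoma: 30 × 0 = 0 to 30 × 0.072 = 2.2

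These bound what could be missed. A hematoma that appears after sheath insertion would be recorded.

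**5. Safety in subjects excluded altogether**

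Suppose 27/30 analysed subjects are free of complications, and k excluded subjects had c complications. The rate with them included is (27 + k − c)/(30 + k). With k = 3:

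- c = 0: 30/33 = 90.9%
- c = 1: 29/33 = 87.9%
- c = 3: 27/33 = 81.8%

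Against the observed 90.0%, leaving them out makes the device look 0.9 points worse in the first case, and 2.1 and 8.2 points better in the other two. The bias favours the device only when c/k exceeds 3/30 = 10%.

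**The case against.** A reader might infer that abandoned procedures become screen failures with no data, that both primary rates are biased upward, and that the enrolment rule contradicts the ITT definition. The documents do not support that much.

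- Section 7.2.1 concerns unacceptable candidates during screening and baseline. It does not name a procedure begun and then stopped, so that subject's status is undefined rather than assigned. The reason for a screen failure is kept, and only further collection stops.
- ITT in 8.3.4 is a subset of enrolled subjects, so it does not contradict 7.3. The two triggers are unreconciled, and the Instructions for Use would be needed to say more.
- A device-inserted efficacy denominator is defensible. The synopsis objective speaks of what the system achieves once in place, and the secondary efficacy endpoint in 8.2.1 runs from insertion into the femoral vein.
- The sheath goes in early. Failures to cross the occlusion or to exit remain in ITT.
- An upward safety bias is not established for wholly excluded subjects (step 5).
- Table 9 does not show how the cited studies defined their denominators. Failure of catheterization belongs to one composite column only. The endpoint is limited to anticipated events, and 5.5 does not name arterial puncture or hematoma as such, although that list is stated not to be exhaustive.
- No performance goal exists, so no decision threshold is crossed.

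All of this stands and narrows the point. It does not answer the start of adverse event recording. Sections 1.3 and 7.4 suggest that access harms would be captured, but 9.0 ties recording to enrolment and 7.3 ties enrolment to insertion. A site following those two sections would omit them.

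**Conclusion.** The point holds as a defect in where counting begins, and it should be corrected. Its firmest part is safety. Read literally, 7.3 and 9.0 leave femoral access harms unrecorded in subjects who are later analysed, for an endpoint that includes procedure-related events. Each missed event is worth 3.3 points in 30 subjects, always in the device's favour. That rests on the literal reading of 9.0 over 1.3 and 7.4, and on the event counting as anticipated.

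The second part is that attempts stopped before insertion have no defined status or follow-up. The efficacy rate is overstated by about 3 points per such attempt only if the target is all attempted procedures. The number of such attempts is assumed.

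**What to change.** 1. Use one enrolment and ITT trigger, in the same words, in 7.2.1, 7.3, 8.1, 8.3.4 and 9.0.
2. Record adverse events from the first femoral puncture for the Surfacer procedure, with 7-day follow-up for every punctured subject. Include any subject found ineligible after puncture, who may remain a screen failure for efficacy. This avoids leaving such subjects without a status.
3. Count pre-insertion procedure-related events in the procedure-related safety endpoint.
4. Report the number of procedures started but stopped before insertion, with reasons and adverse events. Add a sensitivity analysis that counts the eligible subjects among them as efficacy failures.

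The device-inserted set may remain the primary efficacy denominator. The cost is wording in five sections, follow-up of a few extra subjects, and possibly slightly less favourable rates.

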7.3 Subject Enrollment

A subject will be considered “enrolled” in the study when they have completed informed consent, are qualified per all study screening requirements and component of the investigational study device is inserted into the subject.

Once a subject has been exposed to the study device, even if the Investigator is unable to complete the Surfacer treatment, the study subject will be considered part of the intent-to-treat population and will be followed up to 7 days post-procedure, or until any adverse events are resolved.

See Section 8.0 for description of analysis populations and statistical considerations.

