6.3.2 Exclusion Criteria

1. Subjects are contraindicated for Surfacer System use if one of the following are found (per the IFU):
 - a. Occlusion of the right femoral vein;
 - b. Occlusion of the right iliac vein;
 - c. Occlusion of the inferior vena cava.
2. Subjects contraindicated for central venous access based upon the treating physician's opinion and institutional standard of care.
3. Subject has acute thrombosis within any vessel (SVC, jugular, inferior vena cava (IVC), brachiocephalic and subclavian) planned to be crossed by Surfacer System.
4. Subject has tortuous anatomy which precludes a straight line from femoral venous entry to subclavian exit.
5. Subject has been diagnosed with active pericarditis or endocarditis.
6. Subject has a known or suspected pericardial effusion.
7. Subject has a known or suspected aneurysm or ectasia of ascending aorta, innominate artery, or subclavian artery.

8. Subjects who are pregnant or of childbearing potential not taking adequate contraceptive measures or nursing during the study.

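### Sections 7.3 and 8.3.4 conflict on whether a device-exposed subject later found ineligible belongs to the primary ITT set

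*Combined protocol and SAP*

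**What the plan says.** Two passages decide who is in the primary analysis set.

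- **Section 7.3, first paragraph,** sets three conditions for enrollment: consent, qualification and device insertion. The last two read "are qualified per all study screening requirements and component of the investigational study device is inserted into the subject".
- **Section 7.3, second paragraph,** is an exposure rule. It begins "Once a subject has been exposed to the study device, even if the Investigator is unable to complete the Surfacer treatment" and concludes that "the study subject will be considered part of the intent-to-treat population and will be followed up to 7 days post-procedure", or until adverse events resolve. It does not repeat the qualification condition. Section 7.3 then sends the reader to Section 8.0 for the analysis populations.
- **Section 8.3.4** defines the Enrolled Population as consented patients who "complete the screening procedures are eligible and enrolled in the study". The ITT set "comprises all enrolled subjects in whom Surfacer System usage was attempted", whether or not a catheter was placed. Per Protocol is also drawn from enrolled subjects, and it requires a completed procedure.

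Sections 8.3.4 and 8.3.5 make ITT primary for both the safety and the efficacy endpoints.

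**The concern.** Under 8.3.4, membership of ITT passes through the word enrolled, and that word carries an eligibility condition. Under the second paragraph of 7.3, exposure alone is enough. The two rules give different answers for one kind of subject: someone in whom the device was used and who is then found to have met an exclusion.

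That subject is not far-fetched. Contrast angiography and advanced imaging appear only in the intra-procedural column of the schedule (1.3). Section 3.3 has contrast injected to confirm position after the Workstation Sheath has been advanced. The vessels named for the screening ultrasound in 7.2 do not include the femoral or iliac veins, although exclusion 1 covers both. Exclusion 4, "Subject has tortuous anatomy which precludes a straight line from femoral venous entry to subclavian exit", is the clearest case, because anatomy of that kind and a failed pass of the device can look alike in the room.

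This is a single-arm study of 30 subjects with no powered hypothesis (8.2.2), so the observed rates are the evidence. If two readings of the primary set are open, the choice between them could be made after the outcome is known. Subjects treated despite an exclusion are plausibly those more likely to fail or have a complication, so leaving them out would tend to favour the device. The Per Protocol analysis would not reveal the problem, because it is also restricted to enrolled subjects and drops incomplete procedures.

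**Working it through.** **1. The definitions applied to one subject.** Take a subject who consented, passed screening and had a component inserted, and in whom intra-procedural imaging then shows an exclusion.

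- 7.3, second paragraph: exposed, therefore in ITT.
- 8.3.4, with eligibility taken as a matter of fact: not eligible, so not in the Enrolled Population, and therefore in neither ITT nor Per Protocol.
- 8.3.4, with enrollment taken as a status fixed at insertion: enrolled at that time, therefore in ITT.

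No section says which of the last two is meant, or what to do when ineligibility is found after insertion. The screen-failure rule (7.2.1) stops at the point of enrollment and does not settle it.

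**2. The plan's own precision figure.** The exact (Clopper-Pearson) 95% interval for x successes in n subjects is:

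- lower limit = 2.5% quantile of Beta(x, n − x + 1)
- upper limit = 97.5% quantile of Beta(x + 1, n − x)

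With x = 27 and n = 30 (8.2.2) this gives 73.47% to 97.89%, which matches the stated 73.5% to 97.9%. With x = 15 and n = 30 it gives 31.3% to 68.7%, also as stated.

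**3. What removing subjects would do to the efficacy rate.** The number removed is an assumption, because the documents give none. The base is the plan's 27/30 example with its 3 failures.

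| Failures removed (assumed) | Successes/n | Rate | Exact 95% CI |
|---|---|---|---|
| 0 | 27/30 | 90.0% | 73.5 to 97.9 |
| 1 | 27/29 | 93.1% | 77.2 to 99.2 |
| 2 | 27/28 | 96.4% | 81.7 to 99.9 |
| 3 | 27/27 | 100% | 87.2 to 100 |

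Removing one failure raises the rate by 93.1 − 90.0 = 3.1 percentage points and the lower limit by 77.2 − 73.5 = 3.7. If the one subject removed were a success, the rate would become 26/29 = 89.7%, slightly lower. The direction therefore depends on the removed subjects being failures.

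**4. The same for a complication rate.** If the one removed subject had the only complication, 1/30 = 3.3% (upper limit 17.2%) becomes 0/29 = 0% (upper limit 11.9%).

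**The case against.** The strongest reply is that 7.3 fixes enrollment at a point in time. The test is qualification on the screening requirements when the component goes in, not eligibility judged again later. Nothing in the documents un-enrols a subject. The only eligibility-based exit is screen failure, which applies up to enrollment, and 7.6 keeps the data of withdrawn subjects in the analysis. The exposure rule in 7.3 and the ITT wording in 8.3.4 both expressly retain failed procedures. This reading is available and sensible, so a reader who infers that such a subject must drop out of every analysis set goes further than the text. Exclusion is possible under 8.3.4 but not mandated.

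A reader might also infer that adverse-event recording lapses for these subjects, because 9.0 says events are "recorded and assessed from the time of enrolment". The documents do not support that. The phrase sets a start time. Sections 7.4 and 7.5 and the schedule in 1.3 collect adverse events during the procedure, at discharge and at day 7 with no eligibility condition, and 7.3 follows exposed subjects until events resolve.

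The route to a late-found exclusion is also narrower than the list of exclusions suggests. Thrombosis is looked for before the procedure by ultrasound or duplex and by chest imaging (7.2). Femoral access and the exchange wire come before the Workstation Sheath (3.3), so a femoral or iliac occlusion may show before any component is inserted. Tortuous anatomy first seen after insertion remains.

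Finally, the plan states no success threshold for either primary endpoint, so no formal decision would flip. That is correct. It limits the consequence to the reported rates and intervals, which in this study are the result.

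**Conclusion.** The conflict between 7.3 and 8.3.4 is real and concerns the primary analysis set. Applied literally, 8.3.4 permits a device-exposed subject with a late-found exclusion to be left out of ITT and Per Protocol, while the second paragraph of 7.3 keeps that subject in ITT. The documents show neither that anyone would be removed nor that a bias will occur. They show that the question is open and could be answered with the outcome in hand.

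The size cannot be derived from the plan. The illustration, 90.0% rising to 93.1% for one removed failure, assumes the plan's 27/30 example and assumes that the removed subject is a failure. No stated figure in the plan is wrong on this account. Because the correction is a matter of wording and the study is small and uncontrolled, it should be made before the data are analysed.

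**What to change.** - In 8.3.4, define the ITT/safety set as all consented subjects in whom insertion of any Surfacer component was attempted, regardless of whether an eligibility criterion is later found not to have been met. This also gives one trigger for ITT, where 7.3 now uses insertion or exposure and 8.3.4 uses the first step of the Instructions for Use.
- In 8.3.4, remove eligibility as a condition of analysis-set membership.
- In 7.3, keep the eligibility gate for who may be treated, and add that it does not govern analysis-set membership.
- Record an exclusion found after insertion as a protocol deviation, and keep the subject in both primary analyses. Show results without such subjects only as a sensitivity analysis.

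The cost is a few sentences in two sections, with no added subjects, visits or data. The downside for the sponsor is that reported success and safety rates may be slightly less favourable. The plan's sample size and precision figures do not change.
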